1.1 Prevalence and Impact of Asthma

Asthma is one of the most prevalent chronic diseases worldwide, with a substantial burden of disease in the United States. The condition is characterized by extensive airway inflammation leading to variable airflow obstruction, airway hyperresponsiveness and symptoms of wheezing, coughing and dyspnea. Asthma is responsible for an estimated 450,000 hospitalizations in the United States annually (nearly 200,000 of these in children) at considerable cost. Many efforts have been made in attempting to reduce this number. Chronic therapies, consisting primarily of inhaled corticosteroids to reduce airway inflammation and beta-two agonists for acute symptoms, are well recognized by National Heart, Lung, and Blood Institute asthma guidelines for treatment. Despite this, medication adherence remains a major barrier in care.^{5,6}

1.2 ICS Therapy in Asthma

As noted, chronic therapy with ICS is widely recognized as standard of care, first line therapy for patients with persistent asthma. Compared with oral corticosteroids, ICS are effective, safe, and exert a local anti-inflammatory effect directly at the site of pathology. ICS can be delivered by a number of mechanisms, the most common of which are pMDIs, dry powdered inhalers, and nebulizers. Failure to correctly use these devices are a common cause of inadvertent non-adherence and is associated with poor asthma control.⁷⁻¹¹ Nebulization may be an ideal delivery mechanism for very young or old patients, acutely ill patients, or those with neurologic or developmental impairments.¹² Selection of ICS by a physician is an individualized process, with the focus on selecting a product with a delivery device that the patient will be able to use easily as well as a molecule with ideal pharmacokinetics and pharmacodynamics. An ideal ICS would be one that has high lung deposition, prolonged pulmonary residency times and low systemic absorption (reflected by an excellent safety profile).¹³ While beyond the scope of this discussion, comprehensive reviews comparing ICS molecules have been published and are of great reference to the practitioner.¹³

1.3 CFC and HFA Flunisolide

An excellent, comprehensive review of flunisolide was recently published by Melani.¹² Flunisolide was first discovered in 1965 and approved for inhalation via a CFC-MDI in the United States in 1981. Prior studies demonstrated a clinical profile similar to other CFC ICSs such as BDP, fluticasone and budesonide. Lung deposition of this formulation was estimated to be 10% of the delivered dose. Secondary to environmental concerns, CFC MDIs have been phased out with CFC flunisolide being removed from market in 2010. Reformulated versions of these drugs have been developed with HFA MDIs. While some versions of these reformulated drugs were created to match their previous CFC counterparts, others (including flunisolide) were formulated as solutions and deliver extrafine aerosols that have improved deposition even into the distal airways. The mass median aerodynamic diameter of CFC flunisolide was 3.8 μm while the HFA formulation has a MMAD of only 1.2 μm . Studies have demonstrated that this smaller particle size results in significantly less deposition in the mouth, pharynx and GI tract and greater deposition in the peripheral lung with improved homogeneity of deposition throughout the respiratory tract. This results in reduced local side effects such as thrush as well as less systemic bioavailability. HFA flunisolide is FDA approved and has recently been marketed in the US at strength of 80 μg per dose. The device has a 50 mL inhalation chamber attached to assist with medication delivery to the lungs. The recommended starting dose in adults is 160 μg twice daily (recommended maximum dose 320 μg twice daily) and in children (ages 6-11) is 80 μg twice daily (recommended maximum dose 160 μg twice daily).

1.4 Clinical Pharmacology

This section (through 1.6) is derived from data directly from the package insert for flunisolide HFA:

Mechanism of Action: Flunisolide has demonstrated marked anti-inflammatory activity in classical test systems. It is a corticosteroid that is several hundred times more potent than cortisol in animal anti-inflammatory assays, and several hundred times more potent than dexamethasone in anti-inflammatory effect as determined by the McKenzie skin blanching test. The clinical significance of these findings is unknown. The precise mechanism of corticosteroid action is unknown. Airway inflammation is an important component in the pathogenesis

of asthma. Corticosteroids have been shown to have a wide range of anti-inflammatory effects, inhibiting both inflammatory cells (e.g. mast cells, eosinophils, neutrophils, macrophages, and lymphocytes) and release of inflammatory mediators (e.g., histamine, eicosanoids, leukotrienes, and cytokines) involved in allergic and non-allergic mediated inflammation. These anti-inflammatory actions of corticosteroids may contribute to their efficacy in asthma.

Pharmacokinetics: All the data described below is based on studies conducted in subjects 18 to 51 years of age.

Absorption: Flunisolide is rapidly absorbed after oral inhalation. Mean values for the time to maximum concentration, Tmax, of flunisolide range from 0.09 to 0.17 hr after a single 320 mcg dose of AEROSPAN Inhalation Aerosol. The corresponding mean values for the maximum concentration, Cmax, of flunisolide vary from 1.9 to 3.3 ng/mL. Oral bioavailability is less than 7%. Over the dose range of 80 mcg to 320 mcg of

AEROSPAN Inhalation Aerosol, values for Cmax increase proportionately with dose after single as well as multiple dose administration.

Distribution: Flunisolide is extensively distributed in the body, with mean values for apparent volume of distribution ranging from 170 to 350 L after a single 320 mcg dose of AEROSPAN Inhalation Aerosol.

Metabolism: Flunisolide is rapidly and extensively converted to 6 β -OH flunisolide and to water-soluble conjugates during the first pass through the liver. Conversion to 6 β -OH flunisolide, the only circulating metabolite detected in man, is thought to occur via the cytochrome P450 enzyme system, particularly the enzyme CYP3A4. 6 β -OH flunisolide has a low corticosteroid potency (ten times less potent than cortisol and more than 200 times less potent than flunisolide). Maximum levels of 6 β -OH flunisolide were 0.66 mcg/mL after a single 320 mcg dose of AEROSPAN Inhalation Aerosol, and 0.71 mcg/mL after multiple doses of AEROSPAN Inhalation Aerosol.

Excretion: Urinary excretion of flunisolide is low. Less than 1% of the administered dose of flunisolide is recovered in urine after inhalation. The half-life values for 6 β -OH flunisolide range from 3.1 to 5.1 hrs after administration of AEROSPAN Inhalation Aerosol in the dose range of 160 mcg to 320 mcg.

Disposition and Elimination: Twice daily inhalation administration of flunisolide hemihydrate for up to 14 days did not result in appreciable accumulation of flunisolide. Upon multiple dosing with 160 mcg and 320 mcg, the Cmax values were 1.0 ng/mL and 2.1 ng/mL, respectively. The corresponding AUC0-12hr values were 1.2 ng.hr/mL and 2.5 ng.hr/mL.

Flunisolide is rapidly cleared from the body, independent of route of administration or dose administered. Flunisolide is not detectable in plasma twelve hours post-dose. After administration of 320 mcg of AEROSPAN Inhalation Aerosol the elimination half-life ranges from 1.3 to 1.7 hours. After a single 320 mcg dose, mean oral clearance values, not adjusted for bioavailability, range from 83 to 167 L/hr.

Special Populations: There were no gender differences for flunisolide after single and multiple dose administration of the AEROSPAN Inhalation Aerosol. Formal pharmacokinetic studies using flunisolide were not carried out in any other special populations.

Pharmacodynamics: Dose finding for AEROSPAN Inhalation Aerosol was based on comparability of systemic exposure to flunisolide CFC inhalation aerosol. The effect of flunisolide CFC inhalation aerosol and AEROSPAN Inhalation Aerosol on pharmacokinetics and 12-hour plasma cortisol levels was investigated in two studies. In both studies, the Cmax and AUC of flunisolide, 6 β -OH flunisolide, and 12-hour plasma cortisol measurements were comparable for 1000 mcg of flunisolide CFC inhalation aerosol and 320 mcg of AEROSPAN Inhalation Aerosol. The first was a parallel arm study in 31 subjects. Pharmacokinetics and plasma cortisol levels were determined after single and multiple doses of flunisolide CFC inhalation aerosol 1000 μ g and AEROSPAN Inhalation Aerosol 160 μ g or 320 μ g administered twice daily for 13.5 days. At steady state, flunisolide mean peak plasma concentrations from flunisolide CFC inhalation aerosol 1000 mcg and AEROSPAN Inhalation Aerosol 320 mcg were found to be 2.6 ng/mL and 3.4 ng/mL, respectively. The corresponding mean AUC values for the 12-hr dosing interval were 5.7 ng.hr/mL and 4.7 ng.hr/mL, respectively. At steady state, the mean peak plasma concentrations of 6 β -OH flunisolide from flunisolide CFC inhalation aerosol 1000 mcg and AEROSPAN Inhalation Aerosol 320 mcg were found to be 0.9 ng/mL and 0.3 ng/mL, respectively. The corresponding mean AUC values for the 12-hr dosing interval were 3.8 ng.hr/mL and 1.1 ng.hr/mL, respectively. The second was a crossover study in 11 subjects after single doses of flunisolide CFC inhalation aerosol

1000 mcg or AEROSPAN Inhalation Aerosol 320 mcg. The mean peak plasma concentrations of flunisolide from the flunisolide CFC inhalation aerosol 1000 mcg and AEROSPAN Inhalation Aerosol 320 mcg were found to be 2.5 ng/mL and 3.3 ng/mL, respectively. The corresponding mean AUC values were 5.1 ng.hr/mL and 5.8 ng.hr/mL, respectively. The mean peak plasma concentrations of 6 β -OH flunisolide from flunisolide CFC inhalation aerosol 1000 mcg and AEROSPAN Inhalation Aerosol 320 μ g were found to be 0.8 ng/mL and 0.3 ng/mL, respectively. The corresponding mean AUC values were 3.8 ng.hr/mL and 2.3 ng.hr/mL, respectively.

1.5 Pediatric Use of Flunisolide:

The safety and effectiveness of AEROSPAN Inhalation Aerosol has been studied in children 4- 17 years of age. In clinical studies, the efficacy of AEROSPAN Inhalation Aerosol was not established in children 4-5 years of age, although the adverse reaction profile observed in patients exposed to AEROSPAN Inhalation Aerosol was similar between the 4-5 year age group (n=21), the 6-11 year age group (n=210), the 12-17 year age group (n=30), and those patients 18 years of age and older (n=258). The safety and effectiveness of AEROSPAN Inhalation Aerosol has not been studied in patients less than 4 years of age.

Effects on Growth: Controlled clinical studies have shown that orally inhaled corticosteroids may cause a reduction in growth velocity in pediatric patients. In these studies, the mean reduction in growth velocity was approximately one cm per year (range 0.3 to 1.8 cm per year) and appears to depend upon the dose and duration of exposure. This effect was observed in the absence of laboratory evidence of hypothalamic-pituitary-adrenal (HPA) axis suppression, suggesting that growth velocity is a more sensitive indicator of systemic corticosteroid exposure in pediatric patients than some commonly used tests of HPA axis function. The long-term effects of this reduction in growth velocity associated with orally inhaled corticosteroids, including the impact on final adult height, are unknown. The potential for "catch up" growth following discontinuation of treatment with orally inhaled corticosteroids has not been adequately studied. The growth of pediatric patients receiving orally inhaled corticosteroids, including AEROSPAN Inhalation Aerosol, should be monitored routinely (e.g., via

stadiometry). The potential growth effects of prolonged treatment should be weighed against clinical benefits obtained and the risks/benefits of treatment alternatives. To minimize the systemic effects of orally inhaled corticosteroids, including AEROSPAN Inhalation Aerosol, each patient should be titrated to the lowest dose that effectively controls his/her symptoms. The potential effect of AEROSPAN on growth rates in children was assessed in a 52 week randomized, placebo controlled study conducted in 242 prepubescent children age 4 to 9.5 years (145 males, 97 females) with mild persistent asthma. Treatment groups were AEROSPAN 160 mcg twice daily and placebo. Growth velocity was estimated for each patient using the slope of the linear regression of height over time using observed data in the intent to treat population who had at least 3 height measurements. The mean growth velocities were 6.19 cm/year in the placebo group and 6.01 cm/year in the AEROSPAN treated group (difference from placebo -0.17 cm/year; 95% CI: -0.58, 0.24).

1.6 Efficacy of Flunisolide HFA:

The efficacy of AEROSPAN Inhalation Aerosol has been studied in two double-blind, parallel, placebo-and active-controlled clinical trials of 12 weeks duration involving more than 1250 patients, one in adults and adolescents 12 years of age and older, and one in patients 4-11 years of age. In adults and adolescents, efficacy was evaluated in patients previously treated with inhaled corticosteroids. In children 6 to 11 years of age, efficacy was evaluated in patients previously treated with bronchodilators alone or inhaled corticosteroids. Both trials had a 2- week run-in period followed by a 12-week randomized treatment period. During the run-in period all patients received flunisolide CFC inhalation aerosol 500 mcg twice daily. Patients were then randomized to double-blind treatment with different doses of AEROSPAN Inhalation Aerosol or flunisolide CFC inhalation aerosol and monitored for lung function changes to see if they maintained, improved, or lost stability. Baseline was assessed at the end of the run-in period. The primary endpoint was the change from baseline in percent predicted FEV1 after 12 weeks treatment.

Adult and Adolescent Patients 12 Years of Age and Older: Efficacy was evaluated in 669 asthma patients, 12 to 78 years of age, including 88 patients 12-17 years of age and 581 patients 18 years and older. Mean FEV1 at screening was 2.44 L and mean FEV1 at baseline was 2.72 L following the 2-week run-in period. Patients were randomized to AEROSPAN Inhalation Aerosol 80 mcg, 160 mcg or 320 mcg twice daily, flunisolide CFC inhalation aerosol 250 mcg, 500 mcg, or 1000 mcg twice daily, or placebo. Change from baseline in percent predicted FEV1 over 12 weeks treatment demonstrated that placebo patients deteriorated 4.3% from baseline after 12 weeks of treatment, whereas patients treated with AEROSPAN Inhalation Aerosol 160 mcg or 320 mcg twice daily maintained FEV1 over the course of the study. Results for the comparison to placebo were statistically significant for the 160 and 320 mcg twice daily AEROSPAN Inhalation Aerosol doses (see Figure 1), but not for the 80 mcg dose. Secondary endpoints of AM peak expiratory flow rate, AM and PM asthma symptoms, nocturnal awakenings requiring a β 2 agonist, and as needed use of inhaled β 2 agonists showed differences from baseline favoring AEROSPAN Inhalation Aerosol over placebo. AEROSPAN Inhalation Aerosol and flunisolide CFC inhalation aerosol gave comparable results.

Pediatric Patients 4 to 11 Years of Age: The trial enrolled 583 asthma patients, 4 to 11 years of age, although the primary efficacy parameter was evaluated only in the population of 513 patients 6 to 11 years of age. In these patients, the mean FEV1 at screening was 81.2% predicted, and the mean FEV1 at baseline following a two week run-in period was 87.5% predicted. Patients were randomized to

AEROSPAN Inhalation Aerosol 80 mcg or 160 mcg twice daily, flunisolide CFC inhalation aerosol 250 mcg or 500 mcg twice daily, or placebo. Change from baseline in percent predicted FEV1 over 12 weeks in patients 6 years of age and older demonstrated that placebo patients deteriorated 4.0% from baseline after 12 weeks of treatment; whereas patients treated with AEROSPAN Inhalation Aerosol 80 mcg or 160 mcg twice daily maintained FEV1 over the course of the study. Results for the comparison to placebo were statistically significant for the 80 mcg and 160 mcg doses of AEROSPAN Inhalation Aerosol, but there was no added benefit for the 160 mcg BID dose over the 80 mcg BID dose (see Figure 2). AEROSPAN Inhalation Aerosol and flunisolide CFC inhalation aerosol gave comparable results in patients 6 years of age and older.

1.7 Rational for lung function as primary endpoint

We are using change in lung function parameters (FEV1, FEF25-75% from spirometry, R5, R5-R20, AX, Fres from IOS) as a means of assessing response as this provides an objective means of demonstrating improvement in both large and small airways. FEV1 is a well-established parameter in assessing lung function and overall asthma control while FEF25-75% is recognized for its ability to determine small airway obstruction.¹⁴ IOS is an emerging pulmonary function test using sound waves reflected down the pulmonary airway and back designed to assess airway parameters in an effort independent fashion. While the details of its full clinical use is beyond the scope of this article, there are several recent review articles that provide a detailed discussion of the utility of IOS.^{15,16} One key attribute of IOS is that data suggests it may be more sensitive in detecting changes in the small airways than traditional spirometry.¹⁷⁻²⁰ Lung function is routinely used in practice as a means of assessing control and thus these findings will be readily applicable to the clinician. While the pivotal trials of Aerospan looked only at FEV1 changes (a measure of large airway dysfunction), our study proposes to look into small airway function as well.

1.8 Secondary endpoints

Secondary endpoints include asthma symptom control as defined by the standardized asthma control test (ACT). We will also examine the number of corticosteroid courses, ED visits, and admissions patients in each group has over the study period.

2 STUDY RATIONALE

Studies involving the efficacy of flunisolide have primarily been done on the older CFC formulation as discussed above. In addition, none of these studies were targeted at asthma patients specifically with small airway disease. Our goal is to provide greater clarity on the effect of HFA flunisolide at different doses in this unique patient population as HFA flunisolide has a smaller particle size than its CFC predecessor and thus improved deposition in the targeted areas.

3 STUDY OBJECTIVES

3.1 Primary Objective

To assess the impact on lung function of two different doses of HFA flunisolide in asthma patients with small airway disease

4 STUDY DESIGN

4.1 Study Overview

This is a single center, open label, parallel group trial comparing the efficacy of two different strengths of HFA flunisolide on lung function in asthma patients with small airway disease. We will enroll approximately 50 pediatric patients (ages 6-18, see discussion on sample size below) with mild to moderate asthma based upon the National Heart, Lung, and Blood Institute asthma guidelines.²¹ These patients will be recruited from new patients presenting to a pediatric pulmonary clinic as well as from general pediatric clinics associated with the University of Louisville, School of Medicine. Patients will have been steroid-naïve for at least four weeks. Prior to enrollment, patients will have demonstrated small airway disease based on pre-bronchodilator FEF_{25-75%} of less than 65% predicted.²² Patients will be randomized to receive flunisolide at either 80mcg twice a day or 160mcg twice a day with every other consecutive patient receiving alternating therapy (Figure 1). Prior to starting therapy, baseline IOS and spirometry pre and post bronchodilator (BD) will be obtained (Table 1). Patients will be randomized as described above and will be followed up at six weeks. At that point, repeat IOS and spirometry will be obtained again.

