7 STUDY TREATMENTS

7.1 Method of Assigning Subjects to Treatment Groups

We will use a block randomization scheme to promote balance at the end of the study. Block randomization ensures that after each block of individuals are enrolled in the study (n individuals in total); an equal number of individuals will be assigned to each group (n/2 individuals in each group). We will use random block sizes of 8-12. Data about grouping will be kept by study coordinator in a secure, locked location in the clinic. A password protected electronic database will also be created to store patient data in which will be kept on an encrypted, password protected computer.

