9.2 Visit 2 (Baseline) (Day 0)

Subjects who meet eligibility criteria at Visit 1 will be scheduled to return for Visit 2 no sooner than the next day but no later than 56 days following the Screening Visit. The following procedures will be completed:

1. Obtain standardized asthma control score from parent/legal guardian
2. Review current health status/medical history
3. Review concomitant medications
4. Obtain vital signs (temperature, heart rate, respiratory rate and blood pressure)

5. Measure oximetry
6. Measure height and weight
7. Perform abbreviated physical examination (Investigator)
8. Have patient perform IOS pre-bronchodilator
9. Have patient perform spirometry pre-bronchodilator
10. Have patient perform IOS post-bronchodilator
11. Have patient perform spirometry post-bronchodilator

If the subject meets all eligibility:

12. Randomize to flunisolide HFA 80mcg 1 puff BID or flunisolide HFA 80mcg 2 puffs BID
13. Dispense Study Drug and albuterol sulfate with holding chamber.
14. Review instructions for Study Drug administration
15. Schedule subject for Visit 3 (Week 6 ± 1 week)

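### Section 4.1 alternates consecutive patients while section 7.1 uses random permuted blocks; the two rules are incompatible, neither is said to govern, and concealment of the next assignment is not described

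*Combined protocol and SAP*

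**What the plan says.** **Section 4.1 (Study Overview)** describes the study this way: "This is a single center, open label, parallel group trial". It says patients are randomized to 80 mcg or 160 mcg twice daily "with every other consecutive patient receiving alternating therapy (Figure 1"). Later in the same paragraph it adds: "Patients will be randomized as described above and will be followed up at six weeks". Within 4.1, the only description above that sentence is the alternation rule.

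**Section 7.1 (Method of Assigning Subjects to Treatment Groups)** gives a different rule: "We will use a block randomization scheme to promote balance at the end of the study". It requires equal numbers per group in each block and adds: "We will use random block sizes of 8-12". On custody it says: "Data about grouping will be kept by study coordinator in a secure, locked location in the clinic".

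**Section 9.2 (Visit 2)** schedules Visit 2 "no sooner than the next day but no later than 56 days following the Screening Visit". Step 12, after testing and the eligibility check, reads: "Randomize to flunisolide HFA 80mcg 1 puff BID or flunisolide HFA 80mcg 2 puffs BID". It names the arms but gives no method and does not cite 7.1.

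The synopsis and sections 7.2 and 15.1 say only that subjects are randomized or randomly assigned.

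**The concern.** Staff who work from 4.1 and staff who work from 7.1 would run different trials. Under 4.1, anyone who knows the last dose given knows the next one. In an open-label study at one center, that is likely to be everyone involved in enrolment.

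The protocol leaves room to act on that knowledge:

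- The Visit 2 date can fall anywhere from 1 to 56 days after Screening, and section 11 allows a failed Baseline visit to be repeated within that window.
- Several criteria in section 5.2 rest on investigator judgement: ability to comply, upper airway obstruction, and physical findings.

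If the choice of who enrols next depends on the dose that comes next, the arms differ from the start. No planned analysis could reliably remove that bias. The between-dose comparison, which is the trial's main purpose, would lose its basis in randomization.

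A smaller gap remains even if only 7.1 is followed. Locked storage in the clinic says where the grouping data are kept. It does not say who generates the list, whether its holder also enrols patients, or how the next assignment is hidden from the person enrolling.

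**Working it through.** **1. Can the rules coexist?** No figure in the plan depends on the allocation rule, so there is none to reproduce. Alternation fixes every assignment after the first. A permuted block of size *b* draws one of C(*b*, *b*/2) orders at random, and only 2 of these alternate strictly. The chance that one block happens to alternate is 2/C(*b*, *b*/2):

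| Block size | Orders | Chance of strict alternation |
|---|---|---|
| 8 | 70 | 2/70 = 2.9% |
| 10 | 252 | 2/252 = 0.8% |
| 12 | 924 | 2/924 = 0.2% |

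So following 7.1 would almost never produce what 4.1 describes.

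**2. How predictable is the next assignment?** Inputs: 50 recruited (section 15.2), 1:1 allocation (7.1, 7.2), block sizes between 8 and 12 (7.1). Assumption: sizes 8, 10 and 12 are equally likely. Sizes 9 and 11 cannot be split equally, as 7.1 requires.

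- *Alternation:* 49 assignments are certain and the first is a coin flip, so the expected share guessed is (49 + 0.5)/50 = 99.0%. It is 100% if the starting arm is fixed.
- *Random blocks, past assignments visible:* guess the arm with fewer patients so far and flip a coin on ties. About 32.3 of 50 are right, or 64.6%. A guesser who knows the set of sizes but not the current one, and uses that knowledge optimally, does no better (64.6%). On average fewer than one of the 50 assignments (about 0.7 to 0.8) is certain in advance.
- *Fully concealed list:* 50%.

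**3. What could that do to the comparison?** This step is illustrative. In the Blackwell–Hodges guessing model, each enrolment is steered by η SD of the outcome in the direction of the guess. With a share *p* guessed correctly, the difference between arms shifts by 2η(2*p* − 1) SD. The documents give no value for η; 0.10 and 0.25 are assumed.

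- Alternation, η = 0.10: 2 × 0.10 × (1.980 − 1) = 0.196 SD
- Alternation, η = 0.25: 2 × 0.25 × 0.980 = 0.490 SD
- Unconcealed blocks, η = 0.10: 2 × 0.10 × (1.292 − 1) = 0.058 SD
- Unconcealed blocks, η = 0.25: 2 × 0.25 × 0.292 = 0.146 SD

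Section 15.2 expects 40 analysable patients, so take 20 per arm. The noncentrality of the two-sample *t* statistic is the shift × √(20/2), with 38 degrees of freedom. The false-positive rate of a two-sided 5% test, when the doses do not differ, is then:

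| | η = 0.10 | η = 0.25 |
|---|---|---|
| Alternation | 9.3% | 32.7% |
| Random blocks, unconcealed | 5.4% | 7.4% |
| Concealed | 5.0% | 5.0% |

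**The case against.** The strongest reply is that 7.1 plainly governs. Its heading covers exactly this topic, it is the only place that sets out a method in detail, and 4.1 is an overview with one stray clause. The synopsis and sections 7.2, 9.2 and 15.1 all speak of randomization, which fits 7.1. That is a reasonable inference, but the protocol does not state it. Section 4.1 itself uses the word randomized for alternation, so the same word elsewhere does not settle the matter, and 4.1 refers back to its own rule without citing 7.1.

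A second reply is that the error rates rest on an invented amount of steering. This is fair. They need consistent steering at every enrolment, and on six-week change in lung function rather than on baseline severity. They show scale and do not predict what would happen in this trial. The predictability figures do not depend on steering, although the block figure depends on the assumed mix of sizes.

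A third reply is that the concealment gap is minor: 7.1 does keep the grouping data locked away, and even unconcealed blocks raise the error only to 5.4%–7.4% under the same assumptions. This stands. Concealment is a secondary clarification and would not need correction with the same urgency on its own.

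**Conclusion.** The concern holds and must be fixed before allocation starts. Two current sections give incompatible allocation rules and no supplied text ranks them. Figure 1 was not visible in the copy reviewed, so this conclusion rests on the text alone.

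The size depends on which section staff follow. Under 4.1, at least 49 of 50 assignments are known in advance and the trial is not properly randomized. Under 7.1 most of the problem disappears, and what remains is an unstated concealment procedure. The contradiction and the 49 of 50 follow directly from the text; the roughly 65% needs the assumed equal mix of block sizes, and the bias and error figures need the assumed steering.

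**What to change.** **Section 4.1:** replace the alternation phrase with a reference to section 7.1, and check that Figure 1 agrees, so that 7.1 is the only allocation method.

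**Section 7.1:** add wording such as:

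> The 1:1 list will be computer-generated before the first enrolment in permuted blocks of randomly chosen size 8, 10 or 12, and held by a person who neither enrols nor assesses eligibility. Each assignment is revealed, by sequentially numbered sealed opaque envelope or locked electronic list, only at step 12 of Visit 2, after eligibility is recorded.

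Naming the even sizes removes 9 and 11. Another release method would serve equally well if it hides the next assignment from whoever enrols.

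**Section 9.2:** keep the step order, which already places randomization after the eligibility check.

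If any subject has already been assigned, report which method was used. If it was alternation, describe the allocation as quasi-randomized.

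The cost is wording in two sections and one generated list. Visits, sample size and timeline do not change. The one practical burden is that a small single site must find someone outside enrolment to hold the list.
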